20.4.2 Power of primary analysis endpoints

20.4.2.1 The ultimate goal of this research program is to conduct a randomized noninferiority trial to demonstrate that reducing the intensity of therapy in low-risk patients reduces the probability of toxicity while not increasing the probability of tumor recurrence. Such a trial will require hundreds of patients and will be possible only in the cooperative group setting. The purpose of this Phase II trial is to provide preliminary evidence that reduced intensity therapy is practical, and to provide initial evidence of efficacy and toxicity that can be used to design such a trial. The use of the relatively high significance level ($\alpha=0.2$) is not uncommon in early Phase II (e.g., Simon two-stage) trials with limited sample sizes. Out of 33 non-smoking HPV+ patients in the UMCC 2-21 reference set, three patients have died disease-free, and one patient has died from distant metastases. One additional patient in this group has developed a second primary tumor in the oral cavity. All other patients are alive and disease-free. Because the number of events is low, a time-to-event analysis is impractical, and analyses for sub-populations are also unlikely. Because the power will be modest even if the observed failure rates are 2-3 times the control rate, this trial will not definitively test that reduced intensity treatment is as effective as standard chemoradiation, but, if successful, will accrue sufficient data to motivate a true non-inferiority trial.

20.4.2 The power calculations for the toxicity endpoints (Primary Objective 2) will be represented by dysphagia, which is considered the most important. In UMCC 2-21, the patient-reported eating domain score of the HNQOL instrument increased from 10.5 ± 14.9 (mean \pm standard deviation) pre-RT to 25.7 ± 18.9 twelve months after treatment. Videofluoroscopy scores increased from 2.37 ± 1.35 pre-RT to

3.7 ± 1.18 twelve months after treatment. The power of the repeated measures analysis for Primary Objective 2 for these endpoints was assessed by Monte Carlo simulation as the mean twelve month value was reduced from the twelve-month level in UMCC 2-21 (0% decrease) to the baseline UMCC 2- 21 level (100% decrease).

20.4.3 The hypothesis test for Primary Objective 2 will have at least 80% power for the video fluoroscopy score if the reduced intensity treatment achieves a decrease in dysphagia of 58% or greater compared to UMCC 2-21. The power is somewhat lower for the HNQOL assessment.

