3.0 OBJECTIVES

3.1 Primary Objectives

- 3.1.1 To confirm that reducing treatment intensity in patients with HPV related oropharyngeal cancer and ≤ 10 pack-year smoking history by replacing concurrent chemotherapy with concurrent cetuximab, does not significantly increase the proportion of patients whose tumors recur, compared to our previous experience in similar patients receiving chemo-RT.
- 3.1.2 To compare the toxicity in patients receiving cetuximab-RT to similar patients treated with 7 weeks of chemotherapy concurrent with RT ("standard therapy") in UMCC 2-21.

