20.0 STATISTICAL CONSIDERATIONS

20.1 Study Design

This is a Phase II trial of seven weeks RT+cetuximab for head and neck cancer in patients with good prognoses to determine if this treatment will be at least as effective as, but less toxic than, standard therapy. A total of 43 patients will be enrolled in order to obtain 36 patients that complete radiation treatment and have both biopsies taken. Thus, both the clinical primary endpoints and scientific secondary endpoints can be analyzed, as EGFR tumor information is useful for determining potential mechanisms of resistance to cetuximab. Based on the experience of UMCC 9921 and UMCC 2-21, accrual is expected to average one patient per month. To be considered evaluable, a patient must complete the full course of radiation/cetuximab. If radiation and/or cetuximab was stopped or modified due to toxicity, the patient is still evaluable. Inevaluable patients will be replaced.

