20.2 Early Stopping Rules for Toxicity or Lack of Efficacy

In UMCC 9921 and UMCC 2-21, 2/32=6% of patients similar to those who will be treated in the current trial did not achieve tumor control. An early stopping rule will only be feasible for the identification of probability of treatment failure much higher than that. Table 1 describes the stopping rule for failure to control, which was derived using the method due to Thall, Simon and Estey [31], implemented in M.D. Anderson program multc98. **Failure is defined as local-regional recurrence or metastasis, but not second primary cancer, nor microscopic disease found in elective neck dissection, nor PET findings without correlative clinical evidence of disease persistence or recurrence.** For each number of patients enrolled, if *at least* as many failures as stated occurs (e.g., 2/5), accrual will be stopped. The rule was constructed to stop the trial if the probability that the failure rate of the experimental therapy exceeded 0.1625 (0.1 more than the historical rate) is at least 0.75.

# Patients	# Failures
5	2
10	3
15	4
20	5
25	6
30	7

Table 1 Stopping rule for failure to control tumor

Because the trial will only be stopped early for failure, and the stopping rule does not constitute an interim analysis, there will be no adjustment to the p-values of the analyses in Section 20.4.

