20.3 Analysis Plan

20.3.1 Primary Objectives

20.3.1.1 *To confirm that reducing treatment intensity in non-smoking patients with HPV-related oropharyngeal cancer does not significantly increase the proportion of patients whose tumors recur, compared to our previous experience in similar patients receiving standard-intensity chemo-RT.*

The primary index of recurrence will be the proportion of patients who have local recurrence, distant metastases or second primaries (secondary analyses will be performed on each of these endpoints individually) within two years of the end of treatment. In the primary analysis, *null* hypothesis that the proportion of patients who fail is *greater* than 0.20 will be tested using an exact binomial test (at significance level $\alpha=0.20$). The proportion of patients who recur will be calculated, with a 95% exact binomial confidence interval.

20.3.1.2 *To compare the toxicity in patients receiving reduced intensity treatment to similar patients treated with 7 weeks of chemotherapy concurrent with RT ("standard therapy") in UMCC 2-21.*

Dysphagia and mucositis are measured on continuous scales; there are both observer and patient reports. The null hypothesis of no difference in dysphagia and mucositis at three, twelve and twenty-four months posttreatment between the reduced-intensity therapy versus UMCC 2-21 will be tested ($\alpha=0.20$) in a repeated measures analysis of covariance. In addition, the statistical significance of the difference between the current trial and UMCC 2-21 in the proportions of patients experiencing clinically significant (NCI CTCAE Grade 3 or worse) toxicities will be assessed using Fisher's exact test

(a=0.20).

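### The only power statement for the recurrence objective (section 20.4.2.1) has no figure and fits a test for an increase over history, not the planned test against 0.20, whose power is highest when failures are few

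*Combined protocol and SAP*

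**What the plan says.** Section 3.1.1 sets the aim as confirming that de-escalation "does not significantly increase the proportion of patients whose tumors recur, compared to our previous experience". Section 20.3.1.1 turns this into a one-sample test. The null is a failing proportion greater "than 0.20 will be tested using an exact binomial test", at a significance level of 0.20, with a 95% exact interval reported as well. The endpoint is "the proportion of patients who have local recurrence, distant metastases or second primaries", counted over two years from the end of treatment.

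The benchmark is in section 20.2: "2/32=6% of patients similar to those who will be treated in the current trial did not achieve tumor control". Section 20.4.2.1 describes a reference set of 33 patients with one death from distant metastases, and adds: "One additional patient in this group has developed a second primary tumor in the oral cavity". On the section 20.3.1.1 endpoint that is also two events.

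On sample size, section 20.1 says: "A total of 43 patients will be enrolled in order to obtain 36 patients that complete radiation treatment and have both biopsies taken".

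Section 20.4.2.1 defends the high significance level and says that the trial cannot settle whether the two treatments are equally effective, only whether a non-inferiority trial is worth running. Its sole remark on power for recurrence is "Because the power will be modest even if the observed failure rates are 2-3 times the control rate". It states no cut-off, no assumed true rate and no probability of success. By contrast, the stopping rule has a table of operating characteristics (section 20.4.1), and the dysphagia objective has a quantified power statement (section 20.4.3).

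**The concern.** The words *even if* imply that power grows with the failure rate and is still only modest at two to three times control. That is how a test for excess failures behaves. The planned test rejects when failures are few, so its power is greatest at or below the control rate. At two to three times control, its rejection probability is the chance that a regimen with doubled or tripled failures is declared a success.

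Two things are at stake. First, a reader of the power section cannot learn how the efficacy test behaves and may take the trial's limitation to be low power. Second, objective 3.1.1 is worded as a comparison with previous experience. A pass would naturally be reported as no significant increase over about 6%, when the test can show only a rate below 20%. In a de-escalation trial for patients with an excellent prognosis, that difference matters.

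**Working it through.** **Inputs.** Null proportion 0.20, one-sided, alpha 0.20 (section 20.3.1.1). Number analysed: 36 is the target for patients with completed radiation and both biopsies, out of 43 enrolled (section 20.1). The recurrence test needs no biopsy, so 36 to 43 is the possible range. Control rate: 2/32 = 0.0625, stated as 6% (section 20.2), or 2/33 = 0.061 (section 20.4.2.1). Two and three times 6% are 12% and 18%.

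**The plan's own figure.** There is none to reproduce for this test. As a check on inputs, an exact recursion with the Table 1 boundaries gives early-stopping probabilities of 0.046, 0.594, 0.912 and 0.992 at true rates of 0.06, 0.2, 0.3 and 0.4. Table 2 prints 0.05, 0.59, 0.91 and 0.99.

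**Cut-off.** Take the largest c with P(X ≤ c | n, 0.20) ≤ 0.20, where X is binomial. For n = 36:

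- P(X ≤ 4) = 0.0003 + 0.0029 + 0.0128 + 0.0362 + 0.0747 = 0.127.
- P(X ≤ 5) = 0.127 + 0.119 = 0.246, which is too large.

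So c = 4, with attained size 0.127.

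**Probability of success**, P(X ≤ 4 | 36, p):

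- p = 0.06: 0.108 + 0.248 + 0.277 + 0.200 + 0.105 = 0.938
- p = 0.12: 0.010 + 0.049 + 0.118 + 0.182 + 0.204 = 0.563
- p = 0.18: 0.199

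With 2/32 exactly, the values at one and two times control are 0.928 and 0.526.

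**By number analysed, with and without Table 1 stopping.** The stopping columns assume that each outcome is known at once, that the Table 1 failure and the primary endpoint are the same event, and that a stopped trial is not a success.

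| n | cut-off | size | P(success) at 6% / 12% / 18% | size with stopping | P(success) with stopping |
|---|---|---|---|---|---|
| 36 | 4 | 0.127 | 0.94 / 0.56 / 0.20 | 0.116 | 0.91 / 0.53 / 0.18 |
| 38 | 4 | 0.099 | 0.92 / 0.51 / 0.16 | 0.091 | 0.90 / 0.48 / 0.15 |
| 39 | 5 | 0.180 | 0.97 / 0.68 / 0.27 | 0.156 | 0.94 / 0.61 / 0.24 |
| 43 | 5 | 0.115 | 0.96 / 0.59 / 0.19 | 0.102 | 0.92 / 0.54 / 0.17 |

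The cut-off is 4 for n = 36 to 38 and 5 for n = 39 to 43. In every row the probability of success falls steeply as the failure rate rises.

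**Which test would the sentence fit?** Take a Fisher exact test for an increase, 36 new patients against 33 historical ones with a true control rate of 2/33, at alpha 0.20. Its power at two and three times control is 0.33 and 0.64 one-sided, or 0.22 and 0.51 two-sided. That is modest and rises with the failure rate, as the sentence implies. The plan contains no such test for recurrence.

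**Interval beside the test.** At 3/36 and 4/36 the test succeeds, while the 95% exact interval has upper limits of 0.225 and 0.261. The one-sided 80% upper bound, which matches the test, is 0.180 at 4/36.

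**The case against.** The strongest defence is that the sentence is literally true. At two to three times control, the planned test rejects with probability 0.56 down to 0.20, and that can fairly be called modest. The sentence also speaks of observed rates, so it is loose prose and not a formal power claim. This stands as far as it goes: no printed number is wrong. It does not rescue *even if*, because power is about 0.94 at the control rate.

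A second defence is that the caution is already there. The 0.20 null and the high alpha are disclosed, the alpha is justified, and section 20.4.2.1 says that success would only motivate a larger trial. This also stands and limits the harm. The section still attributes the limitation to modest power, and objective 3.1.1 keeps its wording as a comparison with history.

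A third is that Tables 1 and 2 already quantify protection against excess failures. They do so in part, but for early stopping and with a failure definition that leaves out second primaries. They are not power for the final test.

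A reader might infer more than the documents support. Passing at a true 12% is not a type I error, because 12% is below the 0.20 null. Nor does the 95% interval contradict the test when it crosses 0.20. It is a wider, two-sided estimate that the plan does not use as the decision rule.

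**Conclusion.** The point holds as a mis-described and unquantified power statement with a bearing on interpretation. The stated property does not belong to the stated test. At n = 36 the test has high power at the control rate (0.94, or about 0.91 with stopping) and passes a doubled failure rate slightly more often than not (0.56, or about 0.53). The real limitation is the bar: 0.20/0.06 is about 3.3 times the benchmark.

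It would go too far to conclude that the sample size is wrong, that the test is invalid, or that the sponsor presents the trial as definitive. The documents support none of these.

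The figures assume a control rate of about 6% and an analysis set of 36. Over n = 36 to 43, the probability of success at 12% runs from 0.51 to 0.68 without stopping, and from 0.48 to 0.61 with it. The stopping-adjusted values are approximate: outcomes arrive late, and Table 1 excludes second primaries while the endpoint includes them. If the control rate were 1/33 (distant metastasis only), success would have probability 0.996 at that rate and about 0.94 at double, so the size of the problem depends on the benchmark. The direction does not.

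**What to change.** Replace the sentence in section 20.4.2.1 with the rule and its properties:

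- State which patients enter the recurrence test, since 36 is tied to having both biopsies and this test is not.
- Give the cut-off by number analysed (4 for 36 to 38, 5 for 39 to 43) with the attained size.
- Give the probability of success at one, two and three times the control rate with the stopping rule included, and state the assumptions about outcome timing and the failure definition.
- Say in sections 3.1.1 and 20.3.1.1 that success supports a failure rate below 20%, and does not show the absence of an increase from about 6%.
- Optionally, report the one-sided 80% upper bound beside the 95% interval, so that a pass next to an interval crossing 0.20 is explained.

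The cost is protocol and SAP wording. No patients are added, and the test and its null are unchanged. The conclusion available from a positive result becomes less favourable.

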APPENDIX A

KARNOFSKY PERFORMANCE SCALE

100	Normal; no complaints; no evidence of disease
90	Able to carry on normal activity; minor signs or symptoms of disease
80	Normal activity with effort; some sign or symptoms of disease
70	Cares for self; unable to carry on normal activity or do active work
60	Requires occasional assistance, but is able to care for most personal needs
50	Requires considerable assistance and frequent medical care
40	Disabled; requires special care and assistance
30	Severely disabled; hospitalization is indicated, although death not imminent
20	Very sick; hospitalization necessary; active support treatment is necessary
10	Moribund; fatal processes progressing rapidly
0	Dead

APPENDIX B

QUALITY OF LIFE QUESTIONNAIRES

Quality of Life Questionnaire

UMCC 2009.078

Study ID # _____

Initials _____

Completed By: _____

Date Completed _____

Each of the following items lists different numbered statements. Think about what each statement says, then place a circle around the one statement that most closely describes how you have been feeling during the past week, including today. Please circle only one statement for each item.

I. PAIN (General)

A. General

- 10 I have no pain.
- 20 There is mild pain not needing medication.
- 30 I have moderate pain--requires regular medication (codeine or non-narcotic). 40 I have severe pain controlled only by narcotics.
- 50 I have severe pain not controlled by narcotics.

B. Mouth

- 10 I have no pain in my mouth.
- 20 I have mild pain but it is not affecting my eating.
- 30 I have moderate pain which is affecting my eating.
- 40 I have severe pain and need medication in order to eat.
- 50 I have severe pain and cannot eat even with the medication.

C. Throat

- 10 I have no pain in my throat.
- 20 I have mild pain but it is not affecting my eating.
- 30 I have moderate pain which is affecting my eating.
- 40 I have severe pain and need medication in order to eat.
- 50 I have severe pain and cannot eat even with the medication.

II. DISFIGUREMENT

- 10 There is no change in my appearance.
- 20 The change in my appearance is minor.
- 30 My appearance bothers me but I remain active.
- 40 I feel significantly disfigured and limit my activities due to my appearance.
- 50 I cannot be with people due to my appearance.

III. ACTIVITY

- 10 I am as active as I have ever been.
- 20 There are times when I can't keep up with my old pace, but not often.
- 30 I am often tired and I have slowed down my activities although I still get out. 40 I don't go out because I don't have the strength.
- 50 I am usually in a bed or chair and don't leave home.

IV. RECREATION/ENTERTAINMENT

10 There are no limitations to recreation at home and away from home.
20 There are a few things I can't do but I still get out and enjoy life.
30 There are many times when I wish I could get out more but I'm not up to it.
40 There are severe limitations to what I can do, mostly I stay home and watch T.V.
50 I can't do anything enjoyable.

V. EMPLOYMENT

10 I work full time.
20 I have a part time but permanent job.
30 I only have occasional employment.
40 I am unemployed.
50 I am retired (circle one below)
51 not related to cancer treatment
52 due to cancer treatment

VI. EATING

A. Chewing

10 I can chew as well as ever.
20 I have slight difficulty chewing solid foods.
30 I have moderate difficulty chewing solid foods.
40 I can only chew soft foods.
50 I cannot chew soft foods.

B. Swallowing

10 I swallow normally
20 I cannot swallow certain solid foods.
30 I can only swallow soft foods.
40 I can only swallow liquid foods.
50 I cannot swallow.

VII. SALIVA

A. Amount

10 I have a normal amount of saliva
20 I have a mild loss of saliva
30 I have a moderate loss of saliva.
40 I have a severe loss of saliva.
50 I have no saliva.

B. Consistency

10 My saliva has normal consistency.
20 My saliva is slightly thicker.
30 My saliva is moderately thicker.
40 My saliva is extremely thicker.
50 I have saliva that dries in my mouth and/or on my lips.

Study ID: _____

UMCC 2009.078

VIII. TASTE

10 I can taste food normally.
20 I can taste most food normally.
30 I can taste some foods normally.
40 I can taste few foods normally.
50 I cannot taste any foods normally.

IX. SPEECH

10 My speech is the same as always.
20 I have difficulty with saying some words, but can be understood over the phone.
30 I have moderate difficulty saying some words, and cannot use the phone.
40 Only family and/or friends can understand me.
50 I cannot be understood.

X. MUCUS OR PHLEGM

A. Amount

- 10 I have a normal amount of mucus.
- 20 I have a mild amount of mucus
- 30 I have a moderate amount of mucus.
- 40 I have a severe amount of mucus.
- 50 I have no mucus.

B. Consistency

- 10 My mucus has normal consistency
- 20 My mucus is slightly thicker
- 30 My mucus is moderately thicker
- 40 My mucus is extremely thicker
- 50 I have no mucus

Study ID:

UMCC 2009.078

UMCC 2009.078

Study ID # _____

[figure not shown]
Initials _____

Completed By: _____

[figure not shown]
Date Completed _____

Below are several questions that will help describe the dryness in your mouth and how that dryness affects your daily life. Please encircle the number that corresponds to your condition during the last week in each of the following questions:

[figure not shown]
1. Rate the discomfort of our dentures due to dryness (if you do not wear dentures please check)

[figure not shown]
2. Rate the difficulty you experience in speaking due to dryness of your mouth and tongue:

[figure not shown]
3. Rate the difficulty you experience in chewing food due to dryness:

[figure not shown]
4. Rate the difficulty you experience in swallowing food due to dryness:

[figure not shown]
5. Rate the dryness your mouth feels when eating a meal:

[figure not shown]
6. Rate the dryness in your mouth while **not** eating or chewing:

[figure not shown]
7. Rate the frequency of sipping liquids to aid in swallowing food:

8. Rate the frequency of fluid intake required for oral comfort when not eating:

9. Rate the frequency of sleeping problems due to dryness:

10. Does your mouth feel dry when eating a meal? Yes/No

11. Are you thirsty? Yes/No

12. Does the amount of saliva in your mouth seem to be:

- ____ Too little
- ____ Too much
- ____ Don't notice it

13. Do you have difficulties swallowing any food? Yes / No

14. Do you sip liquids to aid in swallowing dry food? Yes / No

15. Have you smoked in the last week? Yes / No

If yes, how many packs? _____

16. Do you drink alcohol more than twice a week? Yes / No

17. Do you have any medical problem/disease for which you take medication? Yes /No

Which pills/medication do you take?

Study ID:

UMCC 2009.078

UMCC 2009.078

Study ID # _____

Initials _____

Completed By: _____

Date Completed _____

INSTRUCTIONS: This survey is designed to assess how much you are bothered by your Head and Neck condition and/or treatment. Please answer every question by marking one box. If you are unsure about how to answer, please give the best answer you can.

1. As a result of your head and neck condition or treatment, over the past FOUR WEEKS how much have you been **BOTHERED** by your...

Not at all Slightly Moderately A lot Extremely

A. Ability to talk to other people
B. Ability to talk on the phone

2. As a result of your head and neck condition or treatment, over the past FOUR WEEKS how much have you been **BOTHERED** by problems with...

Not at all Slightly Moderately A lot Extremely

A. Volume of your voice
B. Clarity of your voice
C. Difficulty opening your mouth
D. Dryness in your mouth while eating
E. Chewing food (for example, pain, difficulty opening or closing your mouth, moving food in your mouth, or teeth or denture problems)
F. Swallowing liquids
G. Swallowing soft foods and/or solids
H. Your ability to taste food (For example, loss of taste, and/or loss of appetite due to poor taste)

I. Pain, burning, and/or discomfort in your mouth, jaw, or throat

J. Shoulder or neck pain

3. Over the past FOUR WEEKS, how often did you take pain medication?...

Never Rarely Sometimes Frequently Always

4. Over the past FOUR WEEKS how much have you been bothered by...

Not at all Slightly Moderately A lot Extremely

A. Concerns or worries about your appearance related to your head and neck condition or treatment

B. Emotional problems related to your head and neck condition or treatment

C. Embarrassment about your symptoms

D. Frustration about your condition

E. Financial worries due to medical problems

F. Worries that your condition will get worse

G. Physical problems related to your head and neck condition

5. Were you working (employed) prior to being diagnosed with cancer? Yes No **If no, go to question 6**

5A. If yes, did your doctor declare you unable to work due to your head and neck condition or treatment? Yes No

6. Have there been other problems related to your head and neck condition that were not mentioned? If so, please write them in the space below and tell us how much this problem has bothered you. (For instance, if your treatment included surgical transfer of tissue from a donor site to the head and neck, does the donor site bother you)

	Not at all	Slightly	Moderately	A lot	Extremely
A. _____					
B. _____					
C. _____					
7. For the past FOUR WEEKS, please rate your OVERALL amount of disturbance or BOTHER as a result of your head and neck cancer condition?					
8. Overall how satisfied are you with your Head and Neck cancer care at this Hospital?					
9. Overall how would you rate your response to treatment?	Poor	Fair	Good	Very Good	Excellent
					
10. Approximately how long did it take you to answer this questionnaire?	_____ Minutes				

11. How difficult was it to
complete this questionnaire?

	Not at all	Slightly	Moderately	A lot	Extremely
	
